4.1.3 Vaccinations

Immunosuppressants may affect the response to vaccination and vaccination during treatment with everolimus may therefore be less effective. The use of live vaccines should be avoided during treatment with everolimus. Patient should also avoid close contact with others who have received live attenuated vaccines. Examples of live vaccines are: intranasal influenza, measles, mumps, rubella, oral polio, BCG, yellow fever, varicella, and TY21a typhoid vaccines.

5 BIOSPECIMEN COLLECTION

5.1 CORRELATIVE STUDIES FOR RESEARCH

5.1.1 Tumor Biopsy

Tumor biopsies (renal primary or metastases or fibrofolliculomas) may be obtained from patients who have easily accessible lesions at baseline and at 8 weeks following initiation of therapy. The biopsies are optional and not required for trial participation. Core or excisional biopsy of an easily accessible sentinel lesion (such as cutaneous/subcutaneous lesions, percutaneously accessible hepatic lesions, lymph nodes etc.) may be performed. Biopsies that are to be used solely for research purposes will be obtained only if they can be performed with minimal risk of complications from the procedure and only after the procedure has been explained to the patient and informed consent obtained. Major surgical procedures such as laparotomy or laparoscopic procedures will not be performed solely to obtain biopsies for research purposes. The biopsies will be performed by members of the interventional radiology, dermatology or surgical staff. Ideally, 2-4 cores will be obtained as long as patient safety is not compromised. A portion of the biopsies will be frozen in liquid nitrogen immediately and transferred to the UOB laboratory (Contact for receiving and processing specimen: [name]/ [name]. - [contact]). Prior to freezing and depending on tissue availability, a small portion of the biopsy specimen may be transferred under sterile conditions to the UOB laboratory to be used to establish a tumor cell line.

Abbreviated Title: Phase II everolimus for BHD

Version Date: March 7, 2017

In addition, attempts will be made to obtain any available archived tumor tissue on all patients to help evaluate FLCN and PTEN/mTOR status and/or components of relevant pathways.

Samples will be processed for the following planned studies. In the event of limited sample availability, we plan to prioritize studies in the order listed below:

- Analysis of somatic FLCN, PTEN, mTOR and other related mutations such as TSC1/2. This will be accomplished by direct sequencing of these genes.
- Analysis of mTOR activity at baseline and comparative analysis in paired pre- and on-treatment tumors when available

Correlative laboratory studies will be performed by investigators in the Urologic Oncology Branch (under the direction of Drs. [name], [name], [name], [name]) and/or Genitourinary Malignancies Branch ([name]'s laboratory) and may involve collaboration with other NIH intramural investigators. Studies listed will be performed wherever possible and as permitted or dictated by clinical outcome and/or sample and resource availability.

5.1.2 Collection, Storage, Use and Disposition of Human Specimens

5.1.2.1 Clinical Samples

Blood and urine samples for clinically relevant, non-research hematology, serum chemistry, urinalysis, and skin biopsy tissue will be prepared using standard procedures. Routine clinical analyses will be performed by the NIH Clinical Center central laboratories or NCI Pathology department. Samples will be processed and disposed according to standard laboratory procedure.

5.1.3 Storage and Research Use of Human Specimens

5.1.3.1 Sample Collection and Planned Research Studies

Research samples will be collected with a view to performing a variety of correlative/biomarker studies (as indicated in Section **5.1**).

5.1.3.2 Sample Processing and Storage

Each patient research sample will be assigned a unique patient identifier and relevant sample characteristics (such as timing of sample collection, treatment cycle and day identifiers) will be recorded. The location of all samples will be carefully tracked in the secure UOB database. All stored samples will be coded and no identifying patient information will be placed on sample containers. Stored samples will be kept in freezers / refrigerators or secure containers located in the Urologic Oncology Branch research laboratories or in the laboratories of collaborators.

Timeframe for research studies: Samples will be stored until requested by an authorized researcher(s). All researchers are required to use the samples for research purposes associated with this trial (as per the NCI IRB approved protocol). Subjects will be given the option of consenting to future use of their research samples per the informed consent process with their option declared in the consent document. Samples from those patients who consent to this will be stored permanently. However, these samples will be used only for research studies on active NCI IRB approved protocols covered by a valid informed consent document. Samples will be

destroyed at the completion of the study from those subjects who decline future use of their samples. Once primary research objectives for the protocol are achieved, intramural researchers can request access to remaining samples provided they have an IRB approved protocol and patient consent. Any unused samples must be returned to the UOB laboratories as appropriate. The PI will report destroyed samples to the IRB if samples become unsalvageable because of environmental factors (e.g. broken freezer or lack of dry ice in a shipping container) or if samples are destroyed because a patient withdraws consent. Samples will also be reported as lost if they are lost in transit between facilities or misplaced by a researcher. Any freezer problems, lost samples or other problems associated with samples will be reported to the IRB, the NCI Clinical Director, and the office of the CCR, NCI.

6 DATA COLLECTION AND EVALUATION

6.1 DATA COLLECTION

Data will be collected prospectively and entered into NCI CCR C3D database. The PI will be responsible for overseeing entry of data into an in-house password protected electronic system and ensuring data accuracy, consistency and timeliness. The principal investigator, associate investigators/research nurses and/or a contracted data manager will assist with the data management efforts. All data obtained during the conduct of the protocol will be kept in secure network drives or in approved alternative sites that comply with NIH security standards. Primary and final analyzed data will have identifiers so that research data can be attributed to an individual human subject participant.

End of study procedures: Data will be stored according to HHS, FDA regulations and NIH Intramural Records Retention Schedule as applicable.

Loss or destruction of data: Should we become aware that a major breech in our plan to protect subject confidentiality and trial data has occurred, the IRB will be notified.

Grade 1 AEs will be excluded.

6.2 RESPONSE CRITERIA

Restaging will be performed approximately every 12 weeks. Treatment can continue for 52 weeks in the absence of unacceptable toxicity or disease progression.

In addition to a baseline scan, confirmatory scans should also be obtained not less than 4 weeks following initial documentation of objective response.

Response and progression will be evaluated in this study using the new international criteria proposed by the revised Response Evaluation Criteria in Solid Tumors (RECIST) guideline (version 1.1).³² Changes in the largest diameter (unidimensional measurement) of the tumor lesions and the shortest diameter in the case of malignant lymph nodes are used in the RECIST criteria.

Abbreviated Title: Phase II everolimus for BHD

Version Date: March 7, 2017

6.2.1 Definitions

Evaluable for toxicity: All patients will be evaluable for toxicity from the time of their first treatment with everolimus.

Evaluable for objective response: Only those patients who have measurable disease present at baseline, have received at least one cycle of therapy, and have had their disease re-evaluated will be considered evaluable for response. These patients will have their response classified according to the definitions stated below. (Note: Patients who exhibit objective disease progression prior to the end of cycle 1 will also be considered evaluable.)

Evaluable Non-Target Disease Response: Patients who have lesions present at baseline that are evaluable but do not meet the definitions of measurable disease, have received at least one cycle of therapy, and have had their disease re-evaluated will be considered evaluable for non-target disease. The response assessment is based on the presence, absence, or unequivocal progression of the lesions.

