1. INTRODUCTION

1.1 STUDY OBJECTIVES

1.1.1 Primary Objective

To determine the overall response rate with everolimus treatment in subjects with BHD-associated renal tumors.

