3 STUDY IMPLEMENTATION

3.1 STUDY DESIGN

This is an open label, phase II study to evaluate the efficacy and safety of everolimus therapy in patients with BHD. Up to 16 evaluable patients will be enrolled.

Patients with BHD typically have bilateral, multifocal tumors localized to the kidneys. In general, the growth rates of these tumors is relatively slow and they are not expected to pose a risk of metastatic spread when the size of the tumors is <3cm. Most of these patients have a surgical option (partial nephrectomy) and are less willing to accept side effects than are patients with metastatic disease. Therefore, everolimus will be administered at a starting dose of 5mg PO QD. If the following criteria are met at the time of the first restaging evaluation, the dose will be escalated to 10mg PO QD.

- A) The patient has not had a complete or partial response, and
- B) The patient has not experienced grade 2 or greater toxicity attributable to everolimus

Restaging will be performed approximately every 12 weeks. Treatment can continue for up to 52 weeks in the absence of unacceptable toxicity or disease progression, except in patients with metastatic RCC associated with BHD in whom everolimus will be continued until disease progression or unacceptable toxicity.

All dosages prescribed and dispensed to the patient and all dose changes during the study must be recorded.

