3.4 STUDY CALENDAR

1 cycle = 28 days

Evaluations below may be performed within \pm 3 days of indicated time in order to accommodate patient schedules, holidays and weather emergencies. Imaging studies and optional tumor biopsies may be performed within \pm 7 days of indicated time.

Baseline and Restaging evaluation will be performed at the NIH CC. However, mandated laboratory studies and other evaluations may be performed at local laboratory or by local health care providers.

Restaging will be performed approximately every 12 weeks. Treatment can continue for 52 weeks in the absence of unacceptable toxicity or disease progression.

Patients with BHD associated tumors localized to the kidneys will be treated for one year in the absence of unacceptable toxicity or disease progression. Patients with locally advanced or metastatic disease will be treated until disease progression in the absence of unacceptable toxicity.

Abbreviated Title: Phase II everolimus for BHD

Version Date: March 7, 2017

	Screening / Baseline	Day 1	Cycle 1 Day 14	Cycle 2 Day 1	Cycle 2 Day 14	Cycle 3 Day 1	Cycle 3 Day 14	Cycle 4 Day 1	Start of Every Cycle	EOT	Follow up ¹¹	Survival ¹²
Visit no.	1	2	3	4	5	6	7	8	9, 10 etc...		EOT + 28 days	
Treatment days	-14 to -1											
Demography/informed consent	X											
Relevant medical history/current medical conditions	X											
Diagnosis and extent of cancer	X											
Vital signs	X	X*		X		X		X	X	X		
Height	X											
Weight	X	X*		X		X		X	X	X	X	
Physical examination	X ⁸											
ECOG/Karnofsky performance status	X	X*										
EKG ¹	X											
Thyroid function tests	X		Every 12 weeks									
CBC with differential	X		X	X		X		X	X	X	X	
Serum Chemistries ²	X		X	X		X		X	X	X	X	
Fasting serum Lipid Profile ³	X			X		X		X	X	X		
Urinalysis ⁴	X			X		X		X	X			
Serum β hCG (in female patients of childbearing potential)	X			X		X		X	X			
HbA1c, pulse oximetry	X											
PT/PTT	X											

Abbreviated Title: Phase II everolimus for BHD

Version Date: March 7, 2017

	Screening / Baseline	Day 1	Cycle 1 Day 14	Cycle 2 Day 1	Cycle 2 Day 14	Cycle 3 Day 1	Cycle 3 Day 14	Cycle 4 Day 1	Start of Every Cycle	EOT	Follow up ¹¹	Survival ¹²
Visit no.	1	2	3	4	5	6	7	8	9, 10 etc...		EOT + 28 days	
Treatment days	-14 to -1											
Prior/concomitant medications	X											
Adverse events												
Tumor evaluation												
PFT	X											
CT chest/abdomen/pelvis and/or, CT chest plus MRI abdomen/pelvis ⁵	X									X		

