3.6.1 Criteria for removal from protocol therapy

- Completion of protocol therapy.
- Progressive disease
- Participant requests to be withdrawn from active therapy
- Unacceptable Toxicity as defined in Section **6.2**.
- Investigator discretion
- Positive pregnancy test

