8 STATISTICAL CONSIDERATIONS

This trial will follow a two-stage minimax design, where 12 patients will be recruited at the first stage. The trial is designed to distinguish between a 5% vs. 25% response rate. If none of the patients respond to therapy, treatment will be deemed ineffective and recruitment for additional patients will be terminated. Otherwise, an additional 4 patients will be recruited in the second stage, yielding a maximum of 16 patients. Treatment will be considered effective if at least 3 patients respond. This will give an 80% power to declare everolimus effective if the response rate is 25% and a 10% type I error if the response rate is 5%. Under this design, the probability of early termination is 54% and the expected sample size is 13.8 if the response rate is 5%.

Up to 16 evaluable patients will be accrued. To allow for inevaluable patients, accrual ceiling will be set at 18. Anticipated duration of study is 2-3 years based on anticipated accrual of 0-1 patient per month.

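### The response set leaves out treated patients who stop in cycle 1 or are never re-imaged; report the rate over all treated patients and keep the two-stage rule

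*Combined protocol and SAP*

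**What the plan says.** The primary objective (Section 1.1.1) is "To determine the overall response rate with everolimus treatment in subjects with BHD-associated renal tumors".

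Section 6.2.1 defines the response set as follows: "Only those patients who have measurable disease present at baseline, have received at least one cycle of therapy, and have had their disease re-evaluated". A note adds patients with objective progression before the end of cycle 1. The toxicity set in the same section has no such filter: "All patients will be evaluable for toxicity from the time of their first treatment with everolimus".

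Section 8 describes a two-stage design: 12 patients, stop if none responds, otherwise 4 more for a maximum of 16. The success rule is a count: "Treatment will be considered effective if at least 3 patients respond". The same section states that the 16 are evaluable patients and adds "To allow for inevaluable patients, accrual ceiling will be set at 18". It gives no denominator and no confidence interval for the reported response rate.

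Three other places bear on who may drop out of the response set:

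- Section 3.1 says that most of these patients have a surgical option and "are less willing to accept side effects than are patients with metastatic disease".
- Section 3.6.1 lists among the reasons for leaving therapy "Participant requests to be withdrawn from active therapy".
- Section 3.4 sets a cycle at 28 days and says "Restaging will be performed approximately every 12 weeks".

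**The concern.** Two groups of treated patients fall outside the response set: those who stop within cycle 1 without objective progression, and those whose disease is never re-imaged. Both exclusions arise after treatment has started. The baseline condition removes nobody who is eligible, because measurable disease is an entry criterion (Section 2.1.1.2).

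Patients who take less than a cycle, or who have no scan, are almost certain not to have a documented response. Leaving them out removes non-responders from the denominator and, apart from the remote case of a response documented after less than one cycle of drug, no responder from the numerator. The bias has one direction: upward. The objective concerns what happens to subjects given everolimus, and stopping early because the drug is not tolerated or not wanted is part of that answer.

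A further gap is that Section 8 names no denominator. The natural reading is the evaluable set, but the choice could still be made after the data are seen. At stake are the reported estimate and its interval.

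**Working it through.** **1. Who is excluded.** The conditions of Section 6.2.1 against the calendar in Section 3.4:

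| Course of the patient | At least one cycle? | Re-evaluated? | In the response set? |
|---|---|---|---|
| Stops in cycle 1, objective progression | no | yes | yes (the note) |
| Stops in cycle 1, no objective progression | no | either | no |
| Stops between about week 4 and week 12, end-of-treatment scan obtained | yes | yes | yes |
| Stops between about week 4 and week 12, no scan | yes | no | no |

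The calendar appears to mark CT/MRI at end of treatment. That scan can rescue the third row but not the second.

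**2. The plan's own design figures.** Inputs from Section 8: n1 = 12, stop at 0 responses; n = 16, success at 3 or more; response rates 5% and 25%.

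- Early termination at 5%: 0.95^12 = 0.540 (stated 54%).
- Expected size at 5%: 12 + (1 − 0.540) × 4 = 13.84 (stated 13.8).
- P(success) = Σ over x = 1 to 12 of P(X1 = x) × P(X2 ≥ 3 − x), with X1 ~ Bin(12, p) and X2 ~ Bin(4, p). At p = 0.25 this is 0.801 (stated 80%). At p = 0.05 it is 0.0427, so the stated 10% is a ceiling and not the attained level.

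The design reproduces.

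**3. Effect on the reported rate.** Section 8 allows 18 − 16 = 2 inevaluable patients. With that allowance the evaluable-only rate exceeds the all-treated rate by a factor of at most 18/16 = 1.125. Exact (Clopper-Pearson) 95% intervals, not adjusted for the two-stage stop:

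| Responders | 16 evaluable | 17 treated (1 inevaluable) | 18 treated (2 inevaluable) |
|---|---|---|---|
| 3 | 18.8% (4.0–45.6) | 17.6% (3.8–43.4) | 16.7% (3.6–41.4) |
| 4 | 25.0% (7.3–52.4) | 23.5% (6.8–49.9) | 22.2% (6.4–47.6) |

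The largest shifts are 18.75 − 16.67 = 2.1 points and 25.0 − 22.2 = 2.8 points. The intervals on 16 patients are 41.6 and 45.1 points wide. With four responders, the denominator decides whether the estimate equals the 25% design target.

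If stage 1 stops with no response, the upper limit is 1 − 0.025^(1/n). For n = 12 it is 26.5%; for n = 14 (2 unassessed patients added) it is 23.2%. The first includes 25% and the second does not.

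**4. Effect on the decision.** Let the all-treated response rate be 5%, let each patient be inevaluable with probability 2/18 (an assumption taken from the ceiling; the documents give no expected rate), and count inevaluable patients as non-responders. Close stage 1 at 12 evaluable patients and end at 16 evaluable or 18 treated. Exact enumeration gives P(success) = 0.0530. Whatever the inevaluable rate, success needs at least 3 responders among at most 18 treated patients, so the bound is P(Bin(18, 0.05) ≥ 3) = 0.0581. Both are below 10%.

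**5. Why the rule should not move to treated patients.** If the 12 and 16 counted the first treated patients, with 11.1% unassessed and a 25% rate among the evaluable, the rate per treated patient would be 0.25 × (1 − 0.111) = 0.222 and power would fall from 80.1% to 72.3%. With 5.6% unassessed (1 in 18) it would be 76.4%.

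**The case against.** The planned primary output is a count rule. Section 8 specifies no evaluable-only percentage, so the bias lies in a reading of the plan and not in a stated calculation. That is fair as far as it goes. But Section 6.2.1 says whose response is classified, Section 8 counts evaluable patients, and no all-treated alternative is given, so the reading is the natural one.

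The likelihood of early stops can also be overstated. Section 3.1 raises reluctance over side effects in order to justify a 5 mg starting dose, and Section 3.3 provides for interruption and reduction before discontinuation. Section 3.5 asks for outside scans when they can be had, and Section 6.2.4.3 asks for effort to document progression after treatment stops. These points make the excluded group smaller. None brings back a patient who stops in cycle 1 without progression.

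The factor of 1.125 holds for the allowance of exactly 2. Under a random rate of 2/18, more than 2 of 18 would be inevaluable with probability 32%, and 15 evaluable of 18 gives 18/15 = 1.2. This stands as a qualification on the size.

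Finally, the fix puts the decision and the main estimate on different denominators. That is true, and it is the reason to report both rates. An evaluable-only count with a declared ceiling is a coherent basis for the accrual rule; it is less suitable as the only reported rate.

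**Conclusion.** The concern holds, and it is minor. The definition excludes treated patients who are almost certainly non-responders, no other section counts them, and the resulting rate can in practice only equal or exceed the all-treated rate.

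At 3 or 4 responders the overstatement is at most 2.1 or 2.8 percentage points with 2 inevaluable patients, which is small beside the intervals. It would be somewhat larger if the ceiling of 18 were reached with fewer than 16 evaluable. The error rate of the decision rule stays below the stated 10%.

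The conclusion rests on two assumptions: that unassessed patients have no documented response, and that the ceiling of 18 is a fair guide to how many there will be.

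**What to change.** Keep the accrual and the rule as they are: 12 evaluable, then 16 evaluable, ceiling 18, effective with at least 3 responders. Say explicitly that the stage 1 count of 12 also means evaluable patients, since Section 8 does not. Then add to Sections 6.2.1 and 8:

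> The response rate and its exact 95% confidence interval are reported over all patients who receive at least one dose of everolimus. Patients with no post-baseline tumor assessment count as non-responders. The rate among patients evaluable for response is a sensitivity analysis.

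The plan should also say whether the interval is adjusted for the two-stage stop; those shown here are not.

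The cost is two or three sentences, with no extra patients and no new data, since every treated patient is already followed for toxicity. With no inevaluable patients, the rule's operating characteristics stay as planned: type I error 4.3%, power 80.1%, and 13.8 evaluable patients expected at a 5% response rate. The one drawback for the sponsor is a slightly lower reported rate.

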6.2.2 Disease Parameters

Measurable disease: Measurable lesions are defined as those that can be accurately measured in at least one dimension (longest diameter to be recorded) as ≥ 20 mm by chest x-ray, as ≥ 10 mm with CT scan, or ≥ 10 mm with calipers by clinical exam. All tumor measurements must be recorded in millimeters (or decimal fractions of centimeters).

Malignant lymph nodes. To be considered pathologically enlarged and measurable, a lymph node must be ≥ 15 mm in short axis when assessed by CT scan (CT scan slice thickness recommended to be no greater than 5 mm). At baseline and in follow-up, only the short axis will be measured and followed.

Non-measurable disease. All other lesions (or sites of disease), including small lesions (longest diameter <10 mm or pathological lymph nodes with ≥ 10 to <15 mm short axis), are considered non-measurable disease. Bone lesions, leptomeningeal disease, ascites, pleural/pericardial effusions, lymphangitis cutis/pulmonitis, inflammatory breast disease, and abdominal masses (not followed by CT or MRI), are considered as non-measurable.

Note: Cystic lesions that meet the criteria for radiographically defined simple cysts should not be considered as malignant lesions (neither measurable nor non-measurable) since they are, by definition, simple cysts.

‘Cystic lesions’ thought to represent cystic metastases can be considered as measurable lesions, if they meet the definition of measurability described above. However, if non-cystic lesions are present in the same patient, these are preferred for selection as target lesions.

Target lesions. All measurable lesions up to a maximum of 2 lesions per organ and 5 lesions in total, representative of all involved organs, should be identified as **target lesions** and recorded and measured at baseline. Target lesions should be selected on the basis of their size (lesions with the longest diameter), be representative of all involved organs, but in addition should be those that lend themselves to reproducible repeated measurements. It may be the case that, on occasion, the largest lesion does not lend itself to reproducible measurement in which circumstance the next largest lesion which can be measured reproducibly should be selected. A sum of the diameters (longest for non-nodal lesions, short axis for nodal lesions) for all target

lesions will be calculated and reported as the baseline sum diameters. If lymph nodes are to be included in the sum, then only the short axis is added into the sum. The baseline sum diameters will be used as reference to further characterize any objective tumor regression in the measurable dimension of the disease.

Non-target lesions. All other lesions (or sites of disease) including any measurable lesions over and above the 5 target lesions should be identified as **non-target lesions** and should also be recorded at baseline. Measurements of these lesions are not required, but the presence, absence, or in rare cases unequivocal progression of each should be noted throughout follow-up.

